FDA	Food and Drug Administration
GI	Gastrointestinal
hrs	hours
HR	Heart Rate
ID	Identification
min	minutes
mm	millimeters
NPV	Negative Predictive Value
PPV	Positive Predictive Value
psi	Pounds per Square Inch pressure unit
PT/INR	Prothrombin Time/International Normalized Ratio
SADE	Serious Adverse Device Effect
SAE	Serious Adverse Event
SOP	Standard Operating Procedures
TASMC	Tel Aviv Sourasky Medical Center
UADE	Unanticipated Adverse Device Effect
USADE	Unanticipated Serious Adverse Device Effect

Date issued:
05 Dec2018

SUBJECT: Functionality and Accuracy of the smART System in Real-Life ICU Settings

Number: CLT3_SY_P001

Revision 08

Page 5 of 38

Synopsis

Study Title:	Functionality and Accuracy of the smART System in Real-Life ICU Settings
Purpose:	To validate the functionality and accuracy of the smART System in areal-life ICU setting
Study Design:	Open, prospective, single arm study
Study Objectives:	
1. To verify that the system is able to automatically detect correct placement and tube movement during on-going use2. To record and analyze impedance levels and reflux episodes3. To verify that the system stops feeding when the tube is misplaced or reflux is detected4. To obtain feedback from clinical staff regarding device use and usability5. To Collect data regarding the occurrence of reflux episodes in relation to patient positioning6. To quantify the amount of discarded nutritional supplement7. To demonstrate the safety of the smART system8. To evaluate the effectiveness of the System to reduce aspiration of gastric contents.
No. of Subjects:	20 subjects
Population:	
- ICU ventilated patients- Patients who are receiving PPI therapy during the study- Patients receiving a standard enteral feeding formula- Patients who are hemodynamically and respiratory stable
Investigational Sites:	Thomas Jefferson University
Principal Investigator:	[name], MD
Study Duration:	56 hrs. -7 days per patient.

smART Healthcare
PATIENT SAFETY THROUGH TECHNOLOGY

Date issued:
05 Dec2018

SUBJECT: Functionality and Accuracy of the smART System in Real-Life ICU Settings

Number: CLT3_SY_P001

Revision 08

Page 6 of 38

Endpoints:	Overall duration of study is estimated to be 3 months (depending on enrollment rate).

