- Impedance sensors, which are made of medical grade SS316 wire. The sensors are located in a number of locations along the feeding tube as well as above the balloon to allow the

system to identify whether it actually prevented the gastric content from climbing up the esophagus.

- Hybrid connector, which has PCB electric contacts and one air conduit – Not in contact with the feeding liquid or the patient body.
- Balloon made of medical grade material.

[figure not shown]

Figure 1: a) smART™ Feeding Tube and feeding connector. b) ENfit connectors for feeding set and GRV Drainage bag connections

1. Y connector- ENFit connection to feeding set
2. Y connector- ENFit connection to GRV Drainage bag
3. smART™ Feeding Tube hybrid connector- feeding tube connection to HUB inlet.
4. smART™ Feeding Tube with Sensors
5. Balloon

b) **Electronic console (12V power supply operated) which:**

- Indicates the location of the tube in the body.
- Inflates and deflates the balloon as needed
- Stops the feeding when feeding tube is out of position during ongoing use.
- Keeps a patient event log The electronic console components include:
- Electronic box, which serves as the interface for the system.

- Stand AC adapter, which allows connecting the electronic console to standard IV stand pole.

c) The Hub:

- The smART™ HUB (Figures 2 and 3) is located at the bedside mounted on a pole. It is connected to the rear panel of the console using a “build in” cable that comes out from the Hub.
- ~~Additional connection between smART™ ENFit feeding inlet of the feeding tube Y connector.~~
- The smART™ Hub has an indicator light that shows the HUB's state

Figure 2: the smART Feeding Tube System

[figure not shown]
[figure not shown]

Figure 3: Pressure Build-Up Safety Mechanism

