4.1 Primary Endpoints

Functionality

- the system is able to accurately guide the user to ensure correct initial placement (verified by X-ray)
- the system is able to detect tube movement/displacement during ongoing use (verified by markings on the tube)
- the system automatically stops feeding when tube displacement is detected
- the system automatically stops feeding when reflux is detected
- the system automatically inflates the balloon when a reflux episode is detected

Safety

- occurrence of device related adverse events

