6.2.2 Treatment

Following the screening procedure staff will utilize the smART System to provide enteral feeding to the patient. Feeding tube insertion and commencement of feeding should be done per patients' need and per local hospital procedures.

6.2.3 Study Specific Procedures:

- Videotaping of subject

Following the completion of the informed consent procedure and prior to feeding tube placement, a video recording of the patient will commence. The camera will be placed across from the patient focusing on the facial area and will allow recording of any movement of the tube for later comparison with the data logs recorded by the smART console. All recorded data must be attached to the CRF and serves as an integral part of the analyzable data for the study.

Specific video procedures will be supplied to the site as part of the study MOP binder.

- Initial Tube Placement:

Vital signs should be noted within 10 minutes of feeding tube insertion.

Study staff should follow the device instructions for use and specific instructions provided by the console during initial tube placement. Time of tube placement is recorded by the console.

Once initial placement is confirmed by the system, verification of correct placement should be performed by abdominal X-ray (gold standard). Note: X-ray should be performed as needed and according to hospital procedures. Once placement confirmation is obtained via x-ray, staff should use a permanent marker to indicate the edge of the nostril on the feeding tube (this mark will enable the staff to verify malpositioning warnings if they occur during on-going use).

- **Ongoing Use**

If system alerts of tube displacement during ongoing use, staff should record the event and verify based on the tube marking if malpositioning occurred and document the event. The need for tube reinsertion/repositioning should be evaluated and performed as needed.

When a reflux episode is detected by the system, the following will be initiated:

1. feeding stops
2. feeding tube balloon will automatically be inflated by the system
3. an alert will sound
4. The Y-piece block opens allowing for feeding system decompression initiating free flow of gastric content into the collection bag. The system will automatically record data relevant to reflux episodes and store it.

- **Feeding Information**

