6.2.6 Study Schedule

Procedures	Screening/ enrollment	Medical Device Placement	Ongoing use	Termination
Day	1	1	Up to 7	2.3 up to 7
Informed Consent	+			
Eligibility Criteria	+			
Physical Exam	+			
Pregnancy test (if applicable)	+			
Vital Signs		+	+	+
Lab Data				+
Medical Device Administration		+	+	
GRV Measurements			+ as needed and according to procedures	
Aspiration of gastric contents recording			+	
Pepsin Test			+ Collected every 8 hrs. during routine tracheal suction	
Adverse Events	+	+	+	+
Concomitant Medication		+	+	+
Patient positioning		+	+	

SUBJECT: Functionality and Accuracy of the smART System in Real-Life ICU Settings

Number: CLT3_SY_P001

Revision 08

Page 23 of 38

Information regarding nutritional supplement administration		+	+	
Patient responses		+	+	
Endoscopy (performed on up to 7 subjects)			+ if blood residue is visible on balloon following tube removal (within 5hrs. of tube removal)	+ On subjects enrolled for a duration of more than 5 days (within 5hrs. of tube removal)

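### The two primary reflux endpoints measure only whether the clamp and balloon act after the console's own detection; no planned analysis measures reflux detection or containment

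*Combined protocol and SAP*

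**What the plan says.** The Synopsis gives the purpose as "To validate the functionality and accuracy of the smART System" in an ICU setting. Section 2.1 adds that the study evaluates the system's ability to keep gastric content from regurgitating into the esophagus.

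Two of the five functionality endpoints in section 4.1 concern reflux: "the system automatically stops feeding when reflux is detected" and "the system automatically inflates the balloon when a reflux episode is detected". Section 6.2.3 (Ongoing Use) identifies the detector: "When a reflux episode is detected by the system, the following will be initiated", followed by the feeding stop, the balloon inflation, an alert and the opening of the decompression path.

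In the same list, initial placement is to be verified by X-ray and displacement detection by the markings on the tube. Neither reflux endpoint names a reference.

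Two other sources bear on reflux:

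- Tracheal samples for a pepsin test, "Collected every 8 hrs. during routine tracheal suction" (section 6.2.6; also 6.2.3 and 6.2.11).
- Impedance sensors above the balloon, placed to allow the "system to identify whether it actually prevented the gastric content from climbing up the esophagus" (section 1.2).

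Section 4.2 includes a literature comparison of aspiration and a correlation of clinical data with reflux occurrence and sensor readings. Section 9.2 lists generic summaries and tests and does not mention missed reflux, agreement or containment. PPV and NPV are in the abbreviation list but are not used in 9.2.

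**The concern.** An endpoint conditional on the device's own detection cannot show how well the device detects. The denominator holds only what the console flagged, so reflux that it missed is invisible. A response to something that was not reflux is scored the same as a response to real reflux.

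What is at stake is interpretation. A result at or near 100% would show that the clamp and balloon follow the console. Beside a purpose that speaks of accuracy and of preventing regurgitation, it could be taken as evidence that reflux is reliably found and held back. The planned analyses give a reader nothing to test that inference against.

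**Working it through.** **The plan's own figure.** Section 9.1 gives 20 subjects and calls this sufficient for the primary endpoint criteria. It states no target rate, precision or error rate, so the figure cannot be reproduced. The argument below does not depend on it.

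**What the endpoint can show.** Let R be the number of true reflux episodes, s the share that the console detects, and F the number of false detections. Suppose the console acts on every detection.

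- Endpoint as written = (sR + F) / (sR + F) = 100%, for any s above 0 and any F.
- Response per true reflux episode = sR / R = s.

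The documents give neither s nor R. For illustration, take R = 100, F = 0 and s from 0.10 to 0.90, with exact (Clopper-Pearson) 95% intervals that treat episodes as independent:

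| Assumed s | Endpoint as written | Response per true episode (95% CI) |
|---|---|---|
| 0.90 | 90/90 = 100% | 90% (82% to 95%) |
| 0.75 | 75/75 = 100% | 75% (65% to 83%) |
| 0.50 | 50/50 = 100% | 50% (40% to 60%) |
| 0.25 | 25/25 = 100% | 25% (17% to 35%) |
| 0.10 | 10/10 = 100% | 10% (5% to 18%) |

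The middle column does not move with s.

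**Whether another endpoint fills the gap.** The endpoint on stopping feeding after displacement has the same conditional form, but a separate endpoint covers displacement detection and names a reference. That reference is itself partial, because section 6.2.3 calls for the marking check when the system alerts. Reflux has no detection endpoint at all.

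**How much pepsin material the schedule yields.** Participation runs from 56 h to 168 h (section 5.3), with one sample per 8 h.

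- Per patient: 56/8 = 7 to 168/8 = 21 samples.
- In 20 completers: 20 × 7 = 140 to 20 × 21 = 420 samples, if every scheduled sample is obtained.

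The 140 is not a floor. Patients can leave before 56 h (section 6.2.12), and suction follows hospital procedure as needed.

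**What a pepsin cross-check could resolve.** The pepsin-positive share is not given. Assuming 5% to 50%, there would be 0.05 × 140 = 7 to 0.50 × 420 = 210 positive samples. The share with no console-logged reflux would have these exact 95% intervals:

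- About 10% unmatched: from 1/7 (14%; 0.4% to 58%) to 21/210 (10%; 6% to 15%).
- About 50% unmatched: from 3/7 (43%; 10% to 82%) to 105/210 (50%; 43% to 57%).

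These intervals ignore clustering within patient, which is likely to make them too narrow.

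**Why the cross-check favours the device.** A positive sample counts as matched if the console logged any reflux in the interval. With three episodes in 8 h and an assumed per-episode sensitivity of 0.50, the chance of at least one detection is 1 − (1 − 0.50)³ = 87.5%.

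**The case against.** The strongest reply is that these are meant as actuation endpoints. They sit under the functionality heading and match objective 3 in section 3, which concerns stopping the feed. The only objective to verify detection (objective 1) concerns placement and tube movement. The purpose line is generic, the study is descriptive, and no success threshold is attached. This stands as a reading of the endpoints, and it is the reason to label them as actuation. It does not remove the mismatch with the accuracy wording in the Synopsis or the regurgitation aim in section 2.1.

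A second reply is that section 4.2 already relates reflux and sensor data to clinical information, which section 6.2.3 says may include laboratory, imaging and respiratory data. So it would be wrong to say that the plan sets nothing outside the device beside the reflux record. But that endpoint defines no measure of missed reflux, false detection or containment, and 9.2 gives no method for it.

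A third reply is that neither available source is a proper reference for detection. This stands in full:

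- Tracheal pepsin marks aspiration. Reflux that never reaches the trachea stays unseen.
- A pepsin-negative interval with a console detection could be a false alarm, successful containment, or reflux without aspiration.
- The above-balloon sensor belongs to the device under test, and a table of inflations is again conditional on detection.
- Section 6.2.3 says that reflux-episode data are stored, but not that this sensor's signal is kept separately.

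A reader might therefore infer that the existing data could validate reflux detection. They could not. They can give a warning sign and a device-reported description.

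**Conclusion.** The concern holds as a limit on what the two endpoints mean. They can read 100% whatever share of reflux is missed, and false detections count as successes. No analysis in section 4 or 9.2 measures reflux detection accuracy or containment, although the stated purpose reaches both. This follows from the endpoint definitions and does not depend on the sample size. The sensitivities, the 100 episodes and the pepsin-positive shares used above are assumptions for illustration.

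A reader might go further and infer that the system misses much reflux, or that a 100% result would be false. The documents support neither: they contain no detection rate in either direction. That a high result would be misread is a risk, not a certainty.

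This should be corrected before the data are analysed. It does not prevent the trial from running.

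**What to change.** 1. In section 4.1 and the Synopsis, word the two endpoints as actuation (feeding stop, balloon inflation) after a console-detected reflux, and state that they do not measure reflux detection accuracy.

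2. Add two descriptive, exploratory analyses to section 9.2:

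   (a) By 8 h sampling interval, the share of pepsin-positive tracheal samples with no console-logged reflux in the preceding interval, with an interval estimate that allows for clustering by patient. Define pepsin-positive and the matching rule in advance, and report how many scheduled samples were obtained. Label it a one-sided warning check for missed reflux that led to aspiration, not an estimate of sensitivity or false alarms. Note that 8 h matching favours the device and that reflux not reaching the trachea is not seen.

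   (b) Among balloon inflations, the share in which the above-balloon sensor still registers content, provided the sponsor confirms that this signal is stored and retrievable. Label it device-reported containment, conditional on detection, and not an independent check of detection. If the signal is not retrievable, say so and omit the table.

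The cost is protocol and SAP wording, time-matching of pepsin results to the console log, and one confirmation from the sponsor. No new procedure, probe or patient is needed.

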4.2 Secondary Endpoints

- Ease of use of the system and the user interface by subjective questionnaire of staff
- Recording of impedance detected by the system and correlation to patient positioning
- Quantification of the amount of discarded nutritional supplement by implementing GRV test as needed and according to hospital procedures
- Reduction of aspiration of gastric contents percentage compared to standard feeding (as reported in literature).
- Correlation between patient clinical information and the occurrence of reflux and sensors data.

5 Study Conduct & Population

This study will be performed in accordance with the design and specific provisions of this protocol, in accordance with the ethical principles that have their origin in the Declaration of Helsinki, that are consistent with Good Clinical Practice (GCP), Title 21 of the Code of Federal Regulations (21 CFR), part 812 (Investigational Device Exemptions), and the applicable regulatory requirements.

SUBJECT: Functionality and Accuracy of the smART System in Real-Life ICU Settings

Number: CLT3_SY_P001

Revision 08

Page 17 of 38

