1.2 Device Description

[figure not shown]
The smART™ Feeding Tube System (sFTS) is a novel system with feeding tube developed by ART Healthcare Ltd, based on sensor-lined tubes that transmit real-time information to an external console. The smART™ feeding tube is equipped with a balloon which serves as an anti-reflux mechanism to prevent the gastric contents from regurgitating to the upper portion of the esophagus thus reducing the risk for aspiration. In addition, the smART™ feeding tube is equipped with sensors designed to provide information about the location of the tube tip relative to the lower esophageal sphincter (LES) thus assisting in reducing the incident of misplacement during first positioning. The smART™ feeding tube is also connected to a motorized mechanism which automatically and in real-time stops feeding if the feeding tube moves out of position during ongoing use or detect gastric content in esophagus. Furthermore, smART™ Feeding Tube System can guide operator to correctly re-position the tube in case of tube migration while feeding.

To minimize the risk of pressure build-up in the stomach and esophagus as a result of the balloon inflation, the company has added an additional safety feature (figure 2). This feature allows for gastric content to escape through the feeding tube into a collection bag. The concept behind this mechanism is simple, once the console detects a reflux episode it automatically stops feeding via clamping and inflates the balloon. The safety feature triggers a release clamp to open, thus allowing gastric content to climb up the feeding tube and release any pressure that may raise within the patients' stomach upper GI tract.

The smART™ Feeding Tube System contains the following (figures 1, 2 and 3):

a) **Feeding tube** – consisting of the following:

- Multi-lumen, made of medical grade material (figure 1a)
- Y-Shaped Feeding inlet, with standard dimensions, made of medical grade material and compatible with ENfit connectors for feeding set and GJV Drainage bag connections, as shown in figure 1b. The Y – Shaped port also connects to a gastric content bag. This feature was added to overcome risks associated with pressure build-up in the stomach and esophagus due to balloon inflation. Gastric contents will pass through the feeding tube and accumulate in the connected collection a bag (figure 2).

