2.3 Residual Risks Associated with the Investigational Device

No residual risk is anticipated with the investigational device.

3 Study Objectives

The primary objectives of this study are:

1. To verify that the system is able to automatically detect correct placement and tube movement during on-going use
2. To record and analyze impedance levels and reflux episodes
3. To verify that the system stops feeding when the tube is misplaced or reflux is detected
4. To obtain feedback from clinical staff regarding device use and usability
5. To Collect data regarding the occurrence of reflux episodes in relation to patient positioning
6. To quantify the amount of discarded nutritional supplement
7. To evaluate the effectiveness of the system to reduce aspiration of gastric contents.

PATIENT SAFETY THROUGH TECHNOLOGY

Date issued:
05 Dec2018

SUBJECT: Functionality and Accuracy of the smART System in Real-Life ICU Settings

Number: CLT3_SY_P001

Revision 08

Page 16 of 38

4 Study Endpoints

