Patient information will be recorded from hospital source at the end of the study for each patient. The information will include feeding times, food amounts and types, medications provided, patient positioning, GRV times and amounts.

- **Gastric Residual Volume (GRV)**

Local site procedure for GRV should be followed as needed and according to hospital procedures. Every occurrence of GRV is supposed to be recorded by the medical staff in hospital sources (according to hospital standards).

- **Patient Positioning**

Every occurrence of patient re-positioning is supposed to be recorded by the medical staff in hospital sources. This information will later be correlated to the occurrence of reflux as recorded by the system.

SUBJECT: Functionality and Accuracy of the smART System in Real-Life ICU Settings

Number: CLT3_SY_P001

Revision 08

Page 20 of 38

- **X-Ray imaging**

Local site procedure for X-ray should be followed as needed and according to hospital procedures. Each time a thorax x-ray image is taken (as part of the patient care). Once feeding tube initial positioning is performed, X-Ray should be taken as part of the usual gold-standard care. A copy of the X-ray should be documented as part of the study CRFs/Forms.

- **Patient general clinical information**

In addition to the CRF's, patient clinical information will be collected directly from the hospital's electronic medical record by the hospital's IT department and provided to the sponsor. The clinical information may include a summary and daily reports and diagnosis, vital signs, imaging data, medications and laboratory reports, breathing and respiratory support parameters, physicians and nurses' notes and medical orders, etc.

The collected information will include valid data from 48 hours prior to feeding tube insertion up until 24 hours after the end of the study.

This information will allow for the analysis of the secondary endpoint dealing with the correlation between patient clinical information and the occurrence of reflux and sensors data.

The data may be collected at various time intervals during the study or at the end of the study once all patients have completed the study.

- **Removal of feeding tube**

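### Discarded supplement is measured by GRV test alone, with no provision to record gastric content that the device vents into its collection bag

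*Combined protocol and SAP*

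**What the plan says.** The aim appears in section 3 (Study Objectives, item 6): "To quantify the amount of discarded nutritional supplement". Section 3 lists it among the primary objectives, while section 4.2 carries the matching endpoint as secondary: "Quantification of the amount of discarded nutritional supplement by implementing GRV test as needed and according to hospital procedures".

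Section 6.2.3 (Ongoing Use) lists what the system does when it detects reflux. Feeding stops, the balloon inflates, an alert sounds, and then: "The Y-piece block opens allowing for feeding system decompression initiating free flow of gastric content into the collection bag". Section 1.2 describes where the fluid goes: "Gastric contents will pass through the feeding tube and accumulate in the connected collection a bag". No return of bag content to the patient is described.

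On data capture, section 6.2.3 (Feeding Information) says: "The information will include feeding times, food amounts and types, medications provided, patient positioning, GRV times and amounts". On GRV it says: "Every occurrence of GRV is supposed to be recorded by the medical staff in hospital sources (according to hospital standards". On the console log it says: "The system will automatically record data relevant to reflux episodes and store it".

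**The concern.** The endpoint is meant to say how much feed is lost. Its only stated measurement is the hospital's GRV test, done when needed. The investigational device adds a loss route that ordinary GRV practice was not written to cover, and the protocol names no measurement for it. If the bag is not read, the component left out is the one the device itself produces, and the omission is largest in patients who vent most.

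The two routes can also interact. Content that has gone into the bag is no longer in the stomach to be aspirated at the next test, so venting may reduce measured GRV while the vented volume goes uncounted. There is no control arm in which such a pattern would show up by contrast. A bag volume not read during the study cannot be recovered afterwards.

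**Working it through.** The documents give no figure for discarded volume, GRV volume, vented volume or reflux frequency, so there is no plan figure to reproduce. The check is mainly a comparison of the places where the bag volume could be captured.

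**1. Where could the bag volume enter the data?**

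| Place | What is there | Bag volume named? |
|---|---|---|
| 4.2, endpoint definition | GRV test | No |
| 6.2.3, Feeding Information | Feeding, medication, position, GRV times and amounts | No |
| 6.2.3, Ongoing Use (console log) | Unspecified reflux data; the only tube sensors described in 1.2 are impedance sensors | No |
| 6.2.6, Study Schedule | Rows for GRV measurements and for supplement administration | No |
| Section 10, items moved to the CRF | Positions, feedings, GRV, vital signs, medication; list left open | No |
| 1.2, Figure 1 legend | Bag port labelled as GRV drainage | Label only, no counting rule |

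**2. Direction of error.** Take volumes of gastric content over the same period:

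- Gd = GRV aspirate that is discarded
- Gr = GRV aspirate that is returned
- B = content vented to the bag and not charted as GRV

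If every GRV amount is counted as discard, the reported value is R = Gd + Gr. The content actually lost is T = Gd + B. The error is R − T = Gr − B.

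- If all aspirate is discarded (Gr = 0), the error is −B. It is downward whenever B > 0 and nil when B = 0.
- If Gr exceeds B, the error is upward.

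The protocol states neither Gr nor B, so the sign is open. Both fluids also mix supplement with secretions. Reading R as pure supplement adds a further upward error, also of unknown size.

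**3. Possible size of the vented component (assumed inputs only).** Assume Gr = 0, discarded GRV aspirate G of 100 to 300 mL/day, 1 to 10 detected episodes a day, and 0 to 50 mL vented per episode. Then B = episodes × volume per episode, and the uncounted share is B/(G + B).

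| G (mL/day) | Episodes/day × mL | B (mL/day) | B/(G + B) |
|---|---|---|---|
| 100 or 300 | any × 0 | 0 | 0% |
| 300 | 1 × 10 | 10 | 10/310 = 3% |
| 300 | 5 × 10 | 50 | 50/350 = 14% |
| 100 | 5 × 10 | 50 | 50/150 = 33% |
| 100 | 10 × 50 | 500 | 500/600 = 83% |

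The range runs from nothing to most of the total. It shows that the omission could matter; it does not estimate it.

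**The case against.** The strongest reply is that the bag may be covered already. The Figure 1 legend labels its port as GRV drainage, and the Feeding Information list speaks of GRV amounts without limiting them to a test. Staff could reasonably chart bag content as GRV. The section 10 list is expressly open, nurses' notes may be drawn from the electronic record, and neither the CRF nor the study manual is in the documents.

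This part stands: a reader might infer that the vented volume will go unrecorded, and the documents do not show that. They show only that the protocol makes no provision to record it. It does not remove the gap, because a label on a figure is not a measurement rule and section 4.2 ties the endpoint to the GRV test. If the bag is meant to count, leaving that unstated allows one nurse to include it and another not.

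A second reply is that little depends on the result. The endpoint is secondary and descriptive, with no comparator group and no success threshold, and sample size and error rates are unaffected. That also stands, and it limits how serious the point is.

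A third reply is that the loss may be trivial. Venting follows only reflux that the system detects, and opening the line permits flow without ensuring it. That stands too, so any range has to start at zero.

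**Conclusion.** The point holds as a gap in the endpoint's measurement rule. As written, section 4.2 leaves out any loss vented by the device, and no section provides for recording it or says whether bag content is GRV. The vented component is undercounted whenever something is vented and not charted as GRV. Its size cannot be determined from the documents and may be zero; the shares above rest wholly on assumed volumes and frequencies.

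A reader might infer that the endpoint is always too low and so favours the device. The documents do not support that. The fate of GRV aspirate is not stated, so counting returned aspirate as discard could outweigh the omitted bag volume, and both fluids contain secretions. Only the vented component has a known direction.

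**What to change.** In section 6.2.3 and the CRF:

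- Record the collection-bag volume at each emptying, at tube change and at tube removal.
- Keep that entry separate from GRV test aspirate. If the site already charts bag content as GRV, adding the two without separation would count it twice.
- For each GRV test, record whether the aspirate was discarded or returned.

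In section 4.2:

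- Define discarded volume as bag volume plus discarded GRV aspirate.
- Report both components and their total.
- Describe them as gastric content that includes supplement, not as supplement alone.

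The cost is a bag reading, a CRF line for it and one extra entry per GRV test. The downside is a little bedside charting. Nothing in patient care or the sample size changes.
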